3.5.7 Patient safety and event reporting

Feasibility and adherence to the discontinuation of imatinib will be reported for all trial subjects. Each GIST patient must be carefully monitored during the course of the protocol. Necessary assessments will include physical examinations, vital signs (systolic/diastolic blood pressure and pulse rate), clinical laboratory tests (haematology, blood biochemistry), and CT/MRI evaluations. CRF reporting after discontinuation of imatinib will be conducted according to the visit schedule. A CRF has to be completed at all visits for the time period the patient is on study after discontinuation of imatinib.

Since there is now study drug in the trial, SAEs related to a study drug cannot be reported.

3.5.8 Potential risks and benefits

When the patient discontinues imatinib, eventual side effects of the medication will disappear. The patient will be followed very closely, and additional radiological examination is performed at each control.

By attending this study and discontinue imatinib the patient may have a greater risk of progression of the disease. However, available data indicate that if a patient develops progression the patient will again achieve stable disease by restarting imatinib.

4 Data management and monitoring

4.1 Case report forms (CRFs)

Data items are collected to the CRFs by the investigators and entered into the electronic study database, located at the OUS secretariat, Oslo, Norway. Principal Investigator is responsible for assuring that data entered into the CRF is complete, accurate, and that entry is performed in a timely manner. The signature or initials of the investigator will attest the accuracy of the data on each CRF. If any assessments are omitted, the reason for such omissions will be noted on the CRFs. Corrections, with the reason for the corrections will also be recorded. Paper CRF will be used in this study.

4.2 Source data

The medical records for each patient should contain information which is important for the patient's safety and continued care, and to fulfill the requirement that critical study data should be verifiable.

To achieve this, the medical records of each patient should clearly describe at least:

- That the patient is participating in the study, e.g. by including the enrollment number and the study code or other study identification;
- Date when Informed Consent was obtained from the patient;
- Results of all assessments confirming a patient's eligibility for the study;
- Diseases (past and current; both the disease studied and others, if relevant);
- Surgical history, as relevant;
- Results of assessments performed during the study;
- WHO performance status assessments conducted as part of the study, if applicable;
- Visits to the clinic / telephone contacts during the study;
- Date of, and reason for, withdrawal from study;
- Date of death and cause of death, if available;
- Additional information according to local regulations and practice

4.3 Study Monitoring

The investigator will be visited based on a monitoring plan (appendix I) by the Clinical Study Monitor, who will check the following:

- Informed consent process
- Adherence to protocol
- Maintenance of required regulatory documents
- The dates of study entry, GIST progression, TKI restarting and death
- Data completion on the CRFs including query resolution and source data verification (SDV).

The monitor will review the relevant CRFs for accuracy and completeness and will ask the site staff to adjust any discrepancies as required.

When the responsible study monitor has checked and verified the CRFs, the data will be entered into a computer database for further handling and statistical evaluation.

Sponsor's representatives (e.g. monitors, auditors) and/or competent authorities will be allowed access to source data for source data verification in which case a review of those parts of the hospital records relevant to the study may be required. Monitoring may be organized locally for each participating country.

5 Central pathology evaluation

The pathology reports from the primary tumour and metastasis will be sent to a Central Pathology Lab of the study located at the OUS, Norway, for evaluation. Tumour tissue samples of any deviant reports will be shipped for secondary review.

5.1 Mandatory pathology information

Immunohistochemistry for CD117 (KIT) and/or DOG-1, and GIST morphology should have been conducted at each clinical site. A representative tumour tissue block will be shipped to the Central Pathology Lab only if a deviant pathology report exists. Collection of tissue for histopathological screening and mutation analyses (*KIT* and *PDGFRA* status) will be done locally during the study. The representative paraffin block will reside at the local hospital for future research purposes.

6 Central radiological review

Radiological tumour assessment at inclusion and at progression should be stored at the local study site and submitted for central secondary review at the OUS, Norway, per request.

7 Molecular and translational studies

The key purpose of the molecular studies is to discover molecular markers that could be used in the prediction of GIST recurrence/progression, and thus in identification of the patients who benefit from life-long imatinib therapy. Blood samples will be shipped to the same Central Laboratory of the study located at the OUS, Norway. The samples will be shipped to the Department of Oncology, Oslo University Hospital, Oslo, Norway; for analyses described below.

7.1 Explorative analyses of GIST-related genes and gene expression

Mutation analysis of genes related to GIST genesis, progression, drug sensitivity, drug resistance, imatinib metabolism or host defence may be carried out from tumour tissue and/or peripheral blood DNA. DNA extracted from the tissue will be analysed for the presence of *KIT* and *PDGFRA* mutations when needed, as well as mutations and expression of other genes deemed important, including genes such as *BRAF*, *RAS*, or gene mutational signatures. An attempt to analyse mutations and gene copy number alterations of a large panel of potentially GIST-related genes and to perform whole exome analysis using next generation sequencing will be made. The results of such future analyses will be correlated to patient outcomes. Besides DNA, RNA and microRNA will be extracted from the tumour tissue, and used for gene expression analyses or other analyses related to the study. The data generated will be linked with the clinical data to study factors associated with GIST progression and recurrence, patient outcome, drug resistance, and host defence.

Protein analyses may also be conducted using paraffin tissue blocks, either using whole sections or tissue microarrays. We will attempt to identify protein or gene aberrations that may be associated with resistance or response to imatinib therapy (such as aberrations related to drug resistance, cell signalling, alternative growth factor receptors, cell cycle progression or apoptosis) or may be associated with patient prognosis and with GIST recurrence (such as cell cycle proliferation rate-related proteins and genes, apoptosis-related proteins and genes, GIST differentiation-related proteins and genes, or host-defence-associated proteins and genes).

7.2 Serum, plasma and whole blood samples

Serum samples (\geq 5 mL of serum) and plasma samples (\geq 5 mL of plasma) are collected longitudinally as indicated in the Visit Schedule (Table 1), and stored at -70°C or colder. A whole blood sample (\geq 5 mL of blood) is collected at baseline. **The baseline samples should be collected when the patient is still on imatinib**.

Samples will be subjected for analysis of serum and plasma proteins, DNA or other molecules relevant to GIST. The serum and plasma protein levels will be correlated with the clinical and outcome data. Samples are collected at the study centres, and shipped on a mutually agreed date to the Central Laboratory (OUS, Oslo, Norway).

A small fraction of the circulated DNA is derived from tumour cells. DNA extracted from plasma samples will be subjected to gene mutation analyses, in particular *KIT* and *PDGFRA* mutations. Plasma samples may also be used for proteomics analyses, and other protein or DNA analyses that might be associated with GIST progression, recurrence, survival or drug resistance. Serum samples are planned to be subjected to analysis of circulating growth factors and to metabolomics assays using mass spectrometry, and of other factors that might be associated with GIST progression, recurrence.

8 Statistical methods

8.1 Sample size and power considerations

The sample size calculation is based on the analysis of the primary objective: PFS at three years after discontinuation of imatinib. PFS is defined as the time interval between the date of discontinuation of imatinib and the date of first detection of GIST progression or death, whichever occurs first. The progression date is defined as the date when the physician first suspects GIST progression in a sequence of events that leads to the diagnosis of progressive GIST. This date will be documented on the CRF by the investigator and will be used as such in the analysis.

The power of the study was derived from comparison to historical controls regarding the main endpoint (PFS). Based on historical data, discontinuation of imatinib in patients with metastatic GIST is associated with rapid recurrence/progression. In the BRF-14 study where patients were randomized to discontinue imatinib at 1 and 3 years of treatment, the 2-years PFS was 10 % and 16 %, respectively. The historical 3-years PFS is expected to be 15 %. An improvement in 3-years PFS from 15 % to 35 % in the study arm is considered clinically significant. To find this effect with 80% power using a one-sided significance level of 0.05, 26 patients are needed. To allow a drop-out rate of 15 %, 31 patients will be included in the trial (power 0.8, one-sided alpha 0.05).

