	 deficiency. 4. Presence of neurofibromatosis-1. 5. R2 resection of the primary tumour or metastasis. 6. Patient with inability to grant reliable informed consent. 7. Inability to comply with the scheduled follow-up. 8. Progressive disease during imatinib or other systemic treatments for GIST before or after surgery/REA of the
STUDY TOEATMENT	metastases. Study group: Discontinuation of imatinib
STUDI IREATMENT	No imatinib or other anti-cancer treatment will be administered.
ASSESSMENTS:	 Primary: Progression-free survival (PFS) is defined by the time interval between the date of imatinib discontinuation and the date of first detection of GIST progression or death, whichever occurs first. Patients alive without progression are censored on the date of last follow-up Secondary:
	 Overall survival (the time period between the date of imatinib discontinuation and the date of death). Quality of Life (EQ-5D instrument).
	 Exploratory: To explore the relationship between study endpoints and blood biomarkers including, but not limited to, KIT/PDGFRA mutations in cell-free circulating DNA in plasma and circulating growth factor and cytokine levels. To explore the relationships between study endpoints and biomarkers in resected tumors prior to study entry. Changes in the blood cell counts and blood biochemistry after stopping imatinib as compared to the values on

	imatinib (includes comparisons in blood cell counts, serum transaminases, creatinine, and electrolytes between the baseline values measured on imatinib and the values measured at 2, 5 and 8 months after stopping imatinib).		
Pre-planned interim analysis:			
	• 1-year PFS in the first 15 patients included. The study is		
	terminated if 10 or more of the 15 patients (≥ 67 %) have		
	progression of disease or withdraws from the study within		
	the first 12 months from the date of study entry.		
STATISTICAL	This is a superiority study as compared with historical controls		
CONSIDERATIONS	regarding the main endpoint (PFS). Based on historical data,		
	discontinuation of imatinib in patients with metastatic GIST is		
	associated with rapid recurrence/progression. In the BRF-14		
	study where patients were randomised to discontinue imatinib at		
	1 and 3 years on treatment, the 2-years PFS was 10 % and 16 %,		
	respectively. Based on these observations, the historical 3-year		
	PFS can be assumed to be 15 %. An improvement in 3-year PFS		

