	from 15 % to 35 % is considered as clinically significant. To find		
	this effect with 80% power using a one-sided statistical		
	significance level of 0.05 , 26 patients are needed. To allow a		
	drop-out rate of 15 %, 31 patients will be included in the trial		
	(power 0.8, one-sided alpha 0.05).		
	-		

Protocol Version Log

Protocol version (date)	Substantial amendment	Changes	Section
V1.0 (13Jun2016)	NA	NA	
V2.0	NA	New Project Manager contact	Contact Details
(24Oct2016)		Addition of Signature Page	Signature Page
		Additional section with potential risks and benefits	3.5.8
V3.0 (20Dec2016)		Added SSG and OUS logo, in addition to EudraCT number and ClinicalTrials.gov identifier	Front page
		Creatinin Kinase deleted	Protocol Synopsis
		Radiological central review included	3.5.3 Tumour assessments and 6 Central Radiological Review
		Adverse Event grade 1-2 included.	3.5.6 Toxicity reporting
V4.0	No	Changed protocol ID / title from "SSG	Front page
(15Mar2017)		XXIV: The Stop-GIST trial" to "SSG XXV: The Stop-GIST trial"	Synopsis
V5.0	Yes	Defined End of Study	3.4.5 End of study
(24Aug2017)		Specified that all amendments to the protocol should also be submitted to competent authorities	11.1.1 Changes to the protocol
		Added Monitoring Plan as appendix I	13 Appendix I

	Screening/ Baseline	Study group					Follow-up (study arm)								
Months from		2	5	8	11	15	19	23	27	31	36	42	48	54	60
randomisation															
Informed consent (a)	0 to -14 d														
Inclusion/ exclusion criteria	0 to -14 d														
Medical history &	0 to -14 d														
demographics (b)															
Regular medication (c)	0 to -14 d														
Adverse events (d)	0 to -14 d														
Physical examination (e)	0 to -14 d	х	Х	х	х	х	х	х	х	х	х	х	х	х	Х
Weight	0 to -14 d	х	Х	х	х	х	х	х	х	х	х	х	х	х	Х
Height	0 to -14 d														
ECOC performance status	0 to -14 d	х	Х	х	х	х	х	х	х	х	х	х	х	х	Х
Haematology (f)	0 to -14 d	х	Х	х	х	х	х	х	х	х	х	х	х	х	Х
Blood biochemistry (g)	0 to -14 d	х	х	х	х	х	х	х	х	х	Х	х	х	х	Х
CT/MRI of the abdomen &	0 to -28 d	х	х	х	х	х	х	х	х	х	Х	х	х	х	Х
pelvis (h)															
Quality of life (i)	0 to -7 d		Х		х		х		х		х		х		Х
Research plasma & serum (j)	0 to -7 d	х	Х	х	х	х	х	х	х	х	х	х	х	х	Х
Research blood (k)	0 to -7 d	X													
Resected metastatic tumour tissue collection (l)						X									

Visit schedule and assessments (Table 1)

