An analysis of the SSGXVIII/AIO trial found that the patients who had GIST recurrence during adjuvant imatinib typically had high tumour cell proliferation rates.⁴⁰ In the subgroup analysis of the same trial, patients who had >10 mitoses within 50 high-power fields (HPFs) of the microscope in the primary GIST benefitted from 3 years of adjuvant imatinib as compared to 1 year of treatment, whereas patients with ≤ 10 mitoses did not.⁴¹ Although subgroup analyses should, in general, be interpreted with great caution, these observations lead to a hypothesis that long imatinib treatments could have a potential to change the biology of GIST to more slowly progressing forms of the disease, as the quickly proliferating GISTs progress early and the rapidly proliferating cancer cells may be more efficiently eradicated by imatinib than the slowly progressing ones. Coupled with the findings from the BRF14 study that suggest that discontinuation of imatinib does not affect overall survival, these observations suggest that imatinib treatment could be discontinued in patients who no longer have macroscopic metastases and who have been on imatinib for many years without rapid recurrence of GIST, and some of such patients might even have been cured from advanced GIST.

In conclusion, we hypothesize that in highly selected patients, i.e. those who have received imatinib for longer than 5 years and who have undergone metastasectomy of all macroscopic oligometastatic disease, stopping imatinib may lead to durable maintained complete remission without the imatinib-associated side effects. Perhaps some GISTs might not recur during the entire life-time of such patients. This hypothesis prompted us to explore the possibility of stopping imatinib in highly selected GIST patients⁴² and now to be further explored in is this prospective clinical trial. The patients will be followed up with frequent imaging after stopping of imatinib, and will have imatinib restarted if GIST recurs. The current study has strict selection criteria of patients, and the patient population is therefore substantially more selected than in the BRF14 trial. Due to the rarity of such highly selected patients, a randomised trial is not considered possible as was the case also in the imatinib discontinuation trials carried out in CML,^{38,39} and an international multicentre design is preferred.

2 Study objectives

Primary objective

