8.3 Efficacy evaluation

Final analysis

The study is designed to investigate the proportion of patients who are alive without GIST progression after a median follow-up of approximately 36 months after study entry.

The primary endpoint PFS will be measured from the date of discontinuation of imatinib to the date of first documentation of progression or death (from any cause), whichever occurs first. Patients alive without GIST progression are censored on the date of last follow-up. Survival estimates will be calculated using the Kaplan-Meier estimator. Comparison between subgroups, if relevant, will be based on the log-rank test and univariate Cox models. Estimates for hazard ratios will be provided with 95% confidence intervals.

The overall subgroup effects will be quantified by a hazard ratio, which will be estimated using a Cox proportional hazards regression model (or a suitable generalisation such as concordance regression, ⁴³ if the model assumptions for the Cox model are not met) with the discontinuation group in the model.

A number of exploratory analyses may be performed for the primary endpoint:

• Log-rank test and Cox proportional hazards model (or a suitable generalisation) stratified by relevant parameters such as, but not limited to the tumour site (gastric or non-gastric),

localization of metastasis (liver, intraperitoneal, both), metachronous and synchronous metastasis.

• A Cox proportional hazard model (or a suitable generalisation) estimating survival while adjusting for the established prognostic variables. In addition, the centre or country and other relevant baseline variables may be included in the model.

Overall survival will be analysed as a secondary endpoint in the final analysis, based on the early data detected by the time of the analysis. Overall survival will be measured from the date of discontinuation of imatinib to the date of death resulting from any cause. Patients alive are censored at the time of last follow-up. Similar methods as for the primary variable will be used in the data analysis.

Exploratory analyses will be carried out to evaluate the data of the molecular analyses carried out. The statistical analyses will be dependent on the biological factors investigated and the analysis methodology used, and will be defined separately for each molecular study.

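### Section 8.1 sizes a one-sided test of 3-year PFS against 15%, but section 8.3 states no comparison with 15% and puts a constant group term in its Cox model

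*Protocol*

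**What the plan says.** The synopsis (Statistical considerations) sets the aim: "This is a superiority study as compared with historical controls", with PFS as the main endpoint. Section 8.1 gives the null, "The historical 3-years PFS is expected to be 15" per cent, and the alternative: "An improvement in 3-years PFS from 15 % to 35 % in the study arm is considered clinically significant". It then states the size: "To find this effect with 80% power using a one-sided significance level of 0.05, 26 patients are needed". Allowing 15% drop-out raises this to 31. Neither place names the test or the formula.

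Section 8.3 defines PFS and its censoring and names the Kaplan-Meier estimator. Log-rank tests and univariate Cox models are for comparing subgroups where relevant. The next paragraph quantifies overall subgroup effects by a Cox hazard ratio "with the discontinuation group in the model". The value 15% does not appear in section 8.3.

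Section 3.1 describes a one-group study, and section 3.4.1 has every patient stop imatinib within 14 days of inclusion.

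For the origin of the 15%, section 8.1 cites 2-year PFS of 10% and 16% in patients of an earlier randomised trial who stopped after 1 and 3 years of imatinib. Section 1.5 says of the present trial that "the patient population is therefore substantially more selected than in the BRF14 trial".

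**The concern.** The sample size section and the analysis section describe different exercises. One is a one-sided superiority test against a fixed rate. The other is estimation plus subgroup comparisons, including a model term that cannot vary. An analysis plan written from section 8.3 would inherit a model that cannot be fitted as described and would find there no statement of what counts as success. In an open-label, single-arm trial of 31 patients, the superiority claim could then be settled after the data are seen.

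Two related points bear on how the result is read. The 15% is presented as the historical 3-year value, yet the figures cited are 2-year values. And the stated power depends on a method that the protocol does not name.

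**Working it through.** **1. Sections 8.1 and 8.3 side by side**

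| Item | Section 8.1 and synopsis | Section 8.3 |
|---|---|---|
| Comparator | fixed 15% | none stated |
| Error rate | one-sided 0.05 | none stated; 95% intervals for hazard ratios |
| Quantity | 3-year PFS | Kaplan-Meier PFS |
| Inference | superiority over history | log-rank and Cox between subgroups; Cox with a discontinuation-group term |

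In a Cox model, a covariate with the same value for every patient cancels from numerator and denominator of each partial-likelihood factor. The likelihood is flat in its coefficient, so no hazard ratio exists. Since all patients stop imatinib, the discontinuation group is such a covariate.

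**2. What the cited history implies**

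PFS cannot rise with time, so 3-year PFS is at most 10% in the 1-year cohort and at most 16% in the 3-year cohort. The 15% exceeds the first bound and lies just under the second. For the 3-year cohort to reach it, 15/16 = 94% of those event-free at 2 years would have to stay so through year 3. If the hazard were constant, which is an assumption the protocol does not make, the values would be 0.10^1.5 = 3.2% and 0.16^1.5 = 6.4%. Either way, 15% is at the upper end of what the figures allow.

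**3. Reproducing the 26 and the 31**

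Inputs from section 8.1: p0 = 0.15, p1 = 0.35, one-sided alpha 0.05, power 0.80, drop-out 15%.

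One-sample normal approximation: n = [(1.645 × √(0.15 × 0.85) + 0.842 × √(0.35 × 0.65)) / 0.20]² = [(0.587 + 0.401) / 0.20]² = 24.4, so 25.

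Power at 26: Φ[(0.20 × √26 − 0.587) / 0.477] = 81.8%.

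Enrolment: 26 / 0.85 = 30.6, so 31.

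The stated 26 is within one patient of this method, and 31 reproduces exactly.

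**4. What that approximation delivers**

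The uncorrected z-test first rejects at 7 of 26: z = (7/26 − 0.15) / √(0.1275/26) = 1.70, above 1.645. At 6 of 26, z = 1.15. Exact binomial tails are:

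| Evaluable | Cut-off | True one-sided alpha | Power at 35% |
|---|---|---|---|
| 26 | at least 7 | 0.083 | 85.8% |
| 26 | at least 8 | 0.032 | 74.0% |
| 28 | at least 8 | 0.049 | 81.8% |
| 31 | at least 9 | 0.034 | 81.1% |

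With 26 complete outcomes, no cut-off gives both alpha at most 0.05 and 80% power. The smallest number that does is 28.

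**5. Under Kaplan-Meier**

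The log-log sample-size formula gives 28 to 30 patients with full follow-up, depending on the variance used. For 31 enrolled, simulation used exponential survival, 15% lost over 36 months and everyone else followed to 36 months. Success was a one-sided 95% lower log-log limit above 15%. Power was about 78-79%.

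**The case against.** The strongest reply is that the protocol already fixes what it must: null, alternative, alpha, sidedness, endpoint, censoring and estimator. The test statistic and the confidence-limit transformation are ordinary content for an analysis plan, which may exist. That stands for the technical detail. It does not cover the Cox term, which is an affirmative statement at odds with the one-group design. Nor does it remove the mismatch, because section 8.3 does describe the inference and leaves out the comparison that section 8.1 was built on.

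Three stronger readings are tempting and should be resisted.

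- A reader might infer that the hazard ratio replaces the primary test. The text ties it to subgroup effects and does not present it as the primary inference.
- A reader might infer that 80% power with 26 patients is an arithmetic error. It reproduces under a standard approximation, and no exact test is promised. The 74% applies only to an exact test on exactly 26 evaluable patients. Kaplan-Meier analysis also uses the follow-up of patients lost early.
- A reader might infer that the 15% invalidates the comparison or makes success too easy. The synopsis and section 8.1 word it as an assumption or expectation, and it is below the 16% cohort's bound. A null at or above the historical value makes the test stricter.

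**Conclusion.** The mismatch between sections 8.1 and 8.3 holds. The firm error is the discontinuation-group term, which is inestimable whatever data arise. Alongside it, the analysis section omits the comparison with 15% for which the trial is sized.

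The 15% needs relabelling, not replacing. It is a chosen threshold at the upper end of what the cited 2-year figures permit, and conservative against those cohorts. Because the protocol describes its own population as more selected, exceeding 15% is best read as exceeding that threshold in this population.

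The power figure is a supporting note. The shortfall when alpha is truly held is about 6 points at 26 evaluable (74% against 80%) and 1 to 2 points for 31 enrolled with 15% loss; at 31 evaluable there is none (81%). These figures take the protocol's 15% and 35% as given and do not model the interim stopping rule. The 78-79% also assumes that everyone not lost reaches 36 months. Section 8.4 requires only a median of 36 months among event-free patients, so earlier censoring could lower it.

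**What to change.** - **Section 8.3, Cox paragraph:** delete "with the discontinuation group in the model" and limit log-rank and Cox analyses to comparisons between baseline subgroups.
- **Section 8.3, primary analysis:** state that the one-sided 95% lower Kaplan-Meier limit for 36-month PFS will be compared with 15%, and that superiority is concluded if the limit exceeds it. Name the transformation there or in the analysis plan; the 78-79% above is for log-log.
- **Section 8.1 and synopsis, threshold:** describe 15% as a chosen threshold. Say that the cited 2-year values cap the 3-year values at 10% and 16%, so that 15% is conservative against history.
- **Section 8.1 and synopsis, power:** name the method behind the 26 and restate the power to match the chosen test: 74% for 26 evaluable (exact, at least 8 of 26), or about 78-79% for 31 enrolled with 15% loss under log-log Kaplan-Meier, with 81% if all 31 are evaluable.

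The cost is wording only, and a stated power slightly less favourable than 80% unless all 31 are evaluable. No patients, visits or assessments are added.
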